12.2 Criteria for Stopping Study

After the first 15 subjects are enrolled, the study will be stopped if 2 or more subjects develop treatment related grade 5 toxicity (death).

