5.1.2 Definition of Dose-Limiting Toxicity

Toxicity and adverse events will be classified according to NCI's Common Terminology Criteria for Adverse Events Version 5.0 (CTCAE v.5).

Dose limiting toxicity (DLT) is defined as one of the following events **that are at least possibly related** to study medications occurring during Cycle 1 (first 28 days):

- Grade 3 or greater hematologic toxicity during the first cycle (28 days) of therapy.
- Cerebrovascular ischemia or cerebrovascular hemorrhage of any duration or grade.
- Grade 3 or greater clinical non-hematological toxicity (excluding \geq grade 3 nausea, vomiting, or diarrhea lasting less than < 72 hours with maximal medical intervention and/or prophylaxis) during the first cycle (28 days) of therapy.
- Delay of Cycle 2 treatment start by more than 2 weeks due to incomplete hematologic recovery ($ANC \geq 1.5 \times 10^9/L$ or platelets $\geq 100 \times 10^9/L$) or unresolved treatment related grade 3 or greater non-hematologic toxicity.
- Grade 2 or greater treatment related neurological toxicity occurring during the first cycle of therapy and lasting more than 72 hours.
- Hepatic labs meeting Hy's Law (concomitant elevations of AST/ALT and bilirubin of 3x ULN and 2xULN respectively without alternative etiology)

DLT's will be counted based on the number of patients with DLT at a given dose level, not the absolute number of DLTs. No single patient can trigger more than one DLT event. Additional patient cohorts will not be enrolled until all patients at the current dose level complete all planned treatment for Cycle 1 and are able to start Cycle 2 with no more than a 2-week delay.

Intra-subject dose escalation is not permitted. Once the MTD of PAC-1 in combination with entrectinib is determined, enrollment will continue until at least 6 subjects total are accrued at the maximum tolerated dose.

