10.1.6 Side Effects

The risks of oral PAC-1 in humans are unknown. However, PAC-1 has shown toxicity in mice, rats, and dogs. In a rat study, deaths occurred in 2 out of 12 rats administered 600 mg/kg/day over a 7-day interval – it should be noted this is a dose over 10 times higher than the planned maximum daily dose to be tested in this trial, 3000 mg (i.e., 50 mg/kg for a 60 kg individual). In one dog study involving repeated oral dosing of PAC-1, gastro-intestinal symptoms were observed (diarrhea, vomiting) accompanied by weight loss. As well, one of the dogs in that study had a seizure that was resolved by administration of diazepam. In another dog study, daily administration of oral PAC-1 at doses of 25 and 50 mg/kg for 28 days was associated with minimal-mild neurodegeneration at multiple sites in the gray matter of the cerebrum. An 84-day oral toxicity and toxicokinetic study of PAC-1 with 1 month and 3 months recovery periods in male and female beagle dogs was recently completed. Daily oral administration (via capsules) of PAC-1 at 6, 13, or 25 mg/kg for 21 consecutive days with a 7-day wash-out period between cycles and repeated for 3 cycles dose-responsive, minimal to mild test article-related vacuolation in different sections of the brains of animals given 13 and 25 mg/kg. The extent and severity of the vacuolization was similar to that seen in the 28-day study. The observed brain vacuolization did not show evidence of recovery after 3 months of being off study drug. No PAC-1 associated neurological or neurocognitive changes have been observed through dose level 7 (750 mg) of Component 1 of phase 1 study NCT02355535.

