12.6 Interim Analysis/Criteria for Stopping Study

No interim analyses are planned for this study. However, the Data Safety Monitoring Board will be reviewing study safety and treatment activity periodically and provide recommendations regarding need for stopping study. See Section 13 for additional information.

13 TRIAL MANAGEMENT**13.1 Data and Safety Monitoring Plan (DSMP)**

HCRN oversight activities include:

- Review and processing of all adverse events requiring expedited reporting as defined in the protocol
- Provide trial accrual progress, safety information and data summary reports to the sponsor-investigator
- Submit data summary reports to the DSMB for review according to DSMB Charter

This study will have a Data and Safety Monitoring Board (DSMB). The DSMB is chaired by an independent medical oncologist external to this trial. The DSMB will provide a recommendation to the sponsor-investigator after all information is reviewed. This information will also be provided to HCRN who will distribute to the site investigator/participating sites for submission to their respective IRB according to the local IRB's policies and procedures.

The DSMB review will include but is not limited to:

- Adverse event summary report
- Audit results if applicable
- Data related to stopping/decision rules described in study design
- Study accrual patterning
- Protocol deviations

The DSMB will meet twice annually during the active study drug administration phase. Additional DSMB meetings may be convened upon request of the Sponsor-Investigator, DSMB, or other applicable oversight body.

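### The only numeric study stopping rule (two treatment-related deaths) is inactive until 15 subjects are enrolled, and the text does not say how earlier deaths count

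*Combined protocol and SAP*

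**What the plan says.** Section 12.2 holds the whole rule: "After the first 15 subjects are enrolled, the study will be stopped if 2 or more subjects develop treatment related grade 5 toxicity (death". It gives no acceptable death rate and no operating characteristics. It does not say how deaths before the fifteenth enrollment are treated.

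The other provisions that bear on early deaths are these.

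- **DLT rule (Sections 5.1.1 and 5.1.2).** It counts events at least possibly related "to study medications occurring during Cycle 1 (first 28 days"). It governs Phase 1b, planned in Section 12.3.1 at 9 to 12 subjects. Its consequences are to expand a cohort or change the dose level; no study stop is stated.
- **Phase 1b to Phase 2 (Section 5.2).** Safety is assessed at the end of Phase 1b. The sponsor-investigator and the two companies review the DSMB's recommendations and decide whether to go on. No numeric criterion is given.
- **Interim review (Section 12.6).** "No interim analyses are planned for this study". The next sentence adds: "However, the Data Safety Monitoring Board will be reviewing study safety and treatment activity periodically and provide recommendations regarding need for stopping study".
- **DSMB meetings (Section 13.1).** "The DSMB will meet twice annually during the active study drug administration phase". Also: "Additional DSMB meetings may be convened upon request of the Sponsor-Investigator, DSMB, or other applicable oversight body".
- **SAE reporting (Sections 11.3.2 and 11.4).** Sites report within 1 business day. The companies and the sponsor-investigator are informed within 1 business day after that.

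**The concern.** The sponsor has named a number of treatment-related deaths at which the study stops, but has tied that number to an enrollment count. The first 14 subjects are those in whom least is known about the combination, and for them the rule is switched off. Two drug-related deaths in Cycle 2 or later would meet the sponsor's own threshold, yet nothing in the text would require a stop. The same holds for two deaths in any cycle among the first new Phase 2 subjects. Enrollment could continue until someone chose to intervene or the fifteenth subject entered.

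The wording is also open to different readings. A monitor and a DSMB could apply 12.2 differently, and would find that out only after a death.

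**Working it through.** The plan states no operating characteristic for the 12.2 rule, so there is no figure to reproduce. The check is a reading of the provisions, followed by an illustration.

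**Step 1. Which rule responds to two treatment-related deaths before subject 15?**

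| Where the deaths fall | Prespecified response | Automatic study stop? |
|---|---|---|
| Phase 1b, Cycle 1 | DLT rule: cohort expansion or change of dose level | None stated |
| Phase 1b, Cycle 2 or later | None (outside the DLT window) | No |
| New Phase 2 subjects before number 15, any cycle | None (DLT rule belongs to Phase 1b) | No |

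New Phase 2 subjects start at number 9 + 1 = 10 or 12 + 1 = 13, depending on the size of Phase 1b. The last row therefore covers subjects 10 to 14 at most and 13 to 14 at least.

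**Step 2. How long is the window?** Total 38 subjects (12.3) over an estimated 18 months (synopsis): 38/18 = 2.1 per month. Fourteen subjects take 14/38 × 18 = 6.6 months, and the fifteenth arrives at 15/38 × 18 = 7.1 months. Phase 1b cohorts wait for Cycle 1 to finish, so it may be later. At two DSMB meetings a year, about one scheduled meeting falls in a window of that length.

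**Step 3. How likely are two deaths among 14 subjects?** The death rate p is an assumption. With n independent, fully followed subjects,

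P(X ≥ 2) = 1 − (1 − p)^n − n·p·(1 − p)^(n−1).

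For n = 14:

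- p = 0.01: 1 − 0.8687 − 0.1229 = 0.008
- p = 0.02: 1 − 0.7536 − 0.2153 = 0.031
- p = 0.05: 1 − 0.4877 − 0.3593 = 0.153
- p = 0.10: 1 − 0.2288 − 0.3559 = 0.415

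These are upper bounds for the uncovered window. They include Cycle 1 deaths in Phase 1b, and deaths among the 14 that occur after subject 15 has enrolled, when the rule is active.

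**Step 4. What does starting the count at the first dose do to the overall chance of stopping?** The same formula applies, and the answer depends on what 12.2 now means.

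| Present meaning of 12.2 | Chance of stopping now, p = 0.02 / 0.05 | With the count from first dose (n = 38) |
|---|---|---|
| Continuous, cumulative count, acting from subject 15 | 0.176 / 0.573 (n = 38) | 0.176 / 0.573 |
| Single look at 15 | 0.035 / 0.171 (n = 15) | 0.176 / 0.573 |

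Under the first reading nothing changes overall, because two early deaths would trigger the rule at subject 15 anyway. Only the timing moves. Under the second reading the chance of stopping rises. A third reading, that only deaths after the fifteenth enrollment count, would ignore early deaths altogether; there too the change could only raise the chance of stopping.

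**The case against.** The strongest reply is that the early period is not unsupervised. The DSMB may recommend stopping and can meet on request. The decision before Phase 2 falls after 9 to 12 subjects and is not confined to Cycle 1 events. SAEs reach the companies and the sponsor-investigator within days. Under the cumulative reading two early deaths still trigger the rule at subject 15, so the defect is a delay.

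Much of this stands. A reader might infer from 12.2 that two early deaths could not stop the trial. The documents do not support that: several parties could stop it. But each of these steps is discretionary or is only a reporting duty, and none carries a numeric trigger. They do not replace a rule the sponsor considered worth fixing in advance.

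A reader might also infer from Section 10.1.6 that toxicity is late and cumulative, so that a Cycle 1 rule is bound to miss it. That section does say of the dogs: "The observed brain vacuolization did not show evidence of recovery after 3 months of being off study drug". But it also reports that the changes in the three-cycle study were similar in extent and severity to those in the 28-day study, which is the length of one cycle. It grades them minimal to mild, and reports no PAC-1-associated neurological or neurocognitive changes in humans through 750 mg. This shows lack of recovery, not late onset, and says little about deaths. The point does not rest on it.

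Finally, the death rates are not from the documents. At 1% or 2% the probability is small.

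**Conclusion.** The point holds as a gap in prespecification. Before 15 subjects are enrolled, no rule would automatically stop the study after two treatment-related deaths outside Cycle 1 of Phase 1b. Section 12.2 also leaves unstated whether earlier deaths count afterwards, and whether the count is continuous or a single look.

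The size depends on an unknown rate: at most 0.008, 0.03, 0.15 and 0.42 at assumed rates of 1%, 2%, 5% and 10%, taking independent subjects with a common rate and full follow-up of all 14. If the present rule is cumulative and continuous, the consequence is delay under discretionary oversight. If it is a single look, or counts later deaths only, the gap is wider. The text does not settle which, and that alone needs correcting.

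**What to change.** In Section 12.2, delete the opening condition on 15 subjects and state the rule along these lines: *From the first dose in Phase 1b onward, the study stops once two subjects have had a grade 5 event judged treatment related; the count is continuous and cumulative over both phases and all cycles.* This keeps the sponsor's threshold of two and its stated consequence, a stopped study, and introduces no new limit.

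If the delay to 15 subjects was intended, 12.2 should instead say why, what applies before then, whether deaths among the first 14 count, and whether the rule is one look or a running count.

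The cost is one sentence and a possible earlier stop. Over 38 subjects the chance of stopping is unchanged (0.18 at 2%, 0.57 at 5%) if the present rule is cumulative and continuous. If a single look at 15 was meant, it rises to those values from 0.035 and 0.17. The sponsor should confirm which was meant before accepting the change.

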12.3 Sample Size and Accrual

Previous studies in the target population identified PFS at 3 months of 38%.⁶ We hypothesize PFS at 3 months of 65%. Controlling for a probability of Type I error at 0.05 (one-sided), our sample size in Phase 2 is estimated to be 32 to ensure 90% statistical power in successfully detecting an alternative PFS rate at 3 months of 0.65, compared to a null rate of 0.38. With 3 additional patients to account for a 10% drop off rate, sample size for phase 2 study will be 35. Sample size analyses were conducted using the PASS software (NCSS, Kaysville, Utah, USA). With phase 1b study component, the study will need to have 3 subjects from Dose Level 1 of Phase 1b + 6 subjects from Dose Level 2 of Phase 1b (and carried over to Phase 2 study). The total number of subjects for the study is 38.

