2.4 Primary Endpoints

2.4.1 Phase 1b

- The MTD of PAC-1 in combination with entrectinib is the highest tested dose of PAC-1 combined with entrectinib with DLT rate of less than 33% in first cycle of therapy (i.e., ≤ 1 out of 6 subjects with DLT).

2.4.2 Phase 2

- PFS at 3 months; this is defined as proportion of alive subjects with metastatic uveal melanoma at 3 months from treatment initiation with PAC-1 in combination with entrectinib without evidence of radiological disease progression by RECIST 1.1.

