12. STATISTICAL CONSIDERATIONS

12.1 Study Design

This is a single arm study.

Phase 1b: The primary objective of the Phase Ib dose escalation cohort study is to establish the MTD of PAC-1 in combination with entrectinib in subjects with metastatic uveal melanoma. A standard “3+3” design will be used to establish the MTD. PAC-1 (PO) will be given daily on Days 1 through 21 of each cycle. Entrectinib (PO) will be given daily on Days 1 through 28 of each cycle. Each cycle will equal 28 days. Response will be evaluated after every 2 cycles. Treatment will continue until disease progression based on RECIST criteria or intolerable toxicity.

Phase 2: The primary objective of the Phase II trial is to estimate 3 months PFS using RECIST v1.1 in subjects with metastatic uveal melanoma treated with PAC-1 in combination with entrectinib. PAC-1 (PO) will be given daily on Days 1 through 21 of each cycle. Entrectinib (PO) will be given daily on Days 1 through 28 of each cycle. Each cycle will equal 28 days. Response will be evaluated after every 2 cycles. Treatment will continue until disease progression based on RECIST criteria or intolerable toxicity. Subjects who voluntarily stop the study, have progressive disease, or unacceptable toxicities will be followed for survival every 2 months for 12 months from start of study treatment, then every 3 months for up to 24 months.

Correlative research analyses include examining the relationship between procaspase 3 expression in archived tumor tissue to degree of clinical response.

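### With 32 subjects, no fixed cut-off on the 3-month PFS count gives both one-sided 5% error and 90% power, and the plan names no test or cut-off

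*Combined protocol and SAP*

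**What the plan says.** Section 12.3, repeated in the synopsis, sets a one-sided type I error of 0.05 and states that "our sample size in Phase 2 is estimated to be 32 to ensure 90% statistical power" for an "alternative PFS rate at 3 months of 0.65, compared to a null rate of 0.38". It continues: "With 3 additional patients to account for a 10% drop off rate, sample size for phase 2 study will be 35". On method it says only that "Sample size analyses were conducted using the PASS software"; neither the PASS procedure nor the test is named.

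Section 2.4.2 makes the Phase 2 primary endpoint a proportion: "this is defined as proportion of alive subjects with metastatic uveal melanoma at 3 months from treatment initiation", without radiological progression. Section 9.9.3 also defines PFS as a right-censored time. Section 12.5.1 plans median PFS with 95% confidence intervals and Kaplan-Meier curves. It gives no comparison with 38% and no success threshold.

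**The concern.** A single-arm study that compares a proportion with a fixed null rate ends in a count: so many of n subjects alive and progression-free at 3 months. If every analyzed subject has a known 3-month status, the Kaplan-Meier estimate at 3 months equals that proportion. Any non-randomised test of the rate then reduces to a cut-off on the count. The stated pair of properties (error at most 5%, power at least 90%) should therefore belong to some cut-off out of 32, and none has both.

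What is at stake is the primary conclusion when the result falls on the boundary. With no test written down, 17 of 32 (53.1%) could be called a success or a failure according to a choice made after the data are seen.

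**Working it through.** **Inputs.** Null rate p0 = 0.38, alternative p1 = 0.65, one-sided alpha 0.05, n = 32, 3 extra subjects for 10% drop-off (all section 12.3); endpoint a proportion (2.4.2).

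**1. The plan's own figure.** The PASS procedure is not stated, so several routes were tried, with z values 1.645 and 1.282.

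- One-sample normal formula: n = [(1.645 × √(0.38 × 0.62) + 1.282 × √(0.65 × 0.35)) / 0.27]² = 27.3, so 28.
- The same with continuity correction: 30.9, so 31.
- Arcsine: 28.6, so 29.
- Exact binomial, first n with error at most 5% and power at least 90%: 29 (16 or more; error 4.51%, power 90.2%).
- Normal test on the log-transformed rate: n = [(1.645 × √(0.62/0.38) + 1.282 × √(0.35/0.65)) / ln(0.65/0.38)]² = 32.1, with nominal power 89.9% at 32.

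So 32 lies within one patient of two recognised formulas and above the others.

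**2. Exact properties at 32.** For a cut-off k, error = P(X ≥ k | 32, 0.38) and power = P(X ≥ k | 32, 0.65).

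| Cut-off | Error | Power |
|---|---|---|
| 17 or more | 5.87% | 94.2% |
| 18 or more | 2.75% | 88.8% |

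Cut-off 18 misses the power by 90 − 88.8 = 1.2 points. Cut-off 17 exceeds the error by 5.87 − 5 = 0.87 points. There is no integer between them.

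**3. What common tests do at 17 of 32.** The observed rate is 17/32 = 0.53125, and the null standard error is √(0.38 × 0.62/32) = 0.0858.

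- Uncorrected z: (0.53125 − 0.38)/0.0858 = 1.763, above 1.645: success.
- Continuity-corrected z: (0.53125 − 0.38 − 1/64)/0.0858 = 1.581, below 1.645: no success. At 18 of 32 it is 1.945, so it needs 18.
- Exact binomial: P(X ≥ 17) = 0.0587, above 0.05: no success.

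The same split occurs at 16 of 30 (true error 6.3%) and 18 of 34 (5.5%).

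**4. Neighboring numbers, exact test.**

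| Analyzed | Critical count | Error | Power |
|---|---|---|---|
| 30 | 17 | 2.91% | 87.4% |
| 31 | 17 | 4.21% | 91.3% |
| 32 | 18 | 2.75% | 88.8% |
| 33 | 18 | 3.93% | 92.3% |
| 34 | 19 | 2.58% | 90.1% |
| 35 | 19 | 3.67% | 93.2% |

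**5. Drop-off.** 32/0.9 = 35.6, and 35 × 0.9 = 31.5. Three subjects in 35 are 3/35 = 8.6%.

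**The case against.** The strongest reply is that some valid 5% tests do exceed 90% power with 32 subjects, so nobody should infer that none exists. An exact test that randomises at 17 with probability 0.721 has error 0.0275 + 0.721 × (0.0587 − 0.0275) = 0.050 and power 0.888 + 0.721 × (0.942 − 0.888) = 0.927. A one-sample log-rank test on 32 subjects followed for 3 months had error 4.0% and power 92.2% in simulation. That run assumed exponential PFS and complete follow-up, neither of which the documents state. Sections 9.9.3 and 12.5.1 do treat PFS as a time to event, so the log-rank route is not far-fetched. This part of the objection stands, and it limits the point to fixed cut-offs on the count. It does not remove the point, because the plan names neither test and the sample-size statement concerns a rate at 3 months.

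Two other inferences are tempting and wrong. One is that normal-theory tests as a class break the error: only the uncorrected z picks 17, and the continuity-corrected z agrees with the exact test. The other is that 32 cannot be reproduced: the corrected normal formula gives 31 and the log-transformed rate gives about 32.

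It is also fair to say that the shortfall is small, that the exact test at 32 spends only 2.75% of its 5%, and that the plan enrolls 35, where exact power is 93.2%. All of that stands. The last figure needs a known 3-month status for all 35, whereas the plan allows for drop-off, and 12.4.2 limits the efficacy set to subjects who were re-evaluated or progressed early. The analyzed number may therefore fall below 35, and the cut-off has to be known for whatever number it is.

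**Conclusion.** The stated combination of one-sided 5% error and 90% power is not delivered by any fixed cut-off on the count out of 32. The plan is 1.2 points short on power (18 or more) or 0.9 points over on error (17 or more). The cause is discreteness, and 31, 33, 34 or 35 analyzed would meet both properties. A reader might conclude that the trial is too small; the documents do not support that, and no patients need to be added.

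The practical weight lies in the missing decision rule. At 30, 32 and 34 analyzed there is a boundary count on which the uncorrected z-test and the exact test disagree, and nothing in 12.3 or 12.5.1 says which governs.

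The drop-off step is a minor matter: 35 keeps 32 subjects up to a loss of 8.6%, not 10%, but 31 analyzed still gives 91.3% power.

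The result assumes independent subjects, a known 3-month status for everyone analyzed, and the rates 0.38 and 0.65 as stated.

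**What to change.** In 12.3, 12.5.1 and the synopsis:

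- Name the exact one-sided binomial test of the 3-month PFS rate against 0.38 as the primary test.
- State the critical count for each number analyzed: 30: 17; 31: 17; 32: 18; 33: 18; 34: 19; 35: 19.
- Restate the operating figures: with 32 analyzed, error 2.75% and power 88.8%; with 35 analyzed and all 3-month statuses known, error 3.7% and power 93.2%.
- Give the drop-off covered by 3 extra subjects as 8.6%, or simply note that 31 analyzed still gives 91.3% power.

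The text should also say which subjects form the denominator and how an unknown 3-month status is counted, since the critical count depends on that number.

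Cost: a few sentences in three places and no added patients. The downside is that the power stated at 32 becomes slightly less favorable.

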STATISTICAL CONSIDERATIONS	
Phase 2 The primary endpoint of the study is 3 month progression-free survival (PFS) rate, using RECIST v1.1, in subjects with metastatic uveal melanoma treated with entrectinib and PAC-1. Kaplan Meier curve will be used to evaluate PFS, and OS; descriptive statistics for response rate, DoR, and toxicity.
 
Sample Size Previous studies in the target population identified PFS at 3 months of 38%.⁶ We hypothesize PFS at 3 months of 65%. Controlling for a probability of Type I error at 0.05 (one-sided), our sample size in Phase 2 is estimated to be 32 to ensure 90% statistical power in successfully detecting an alternative progression free survival rate at 3 months of 0.65, compared to a null rate of 0.38. With 3 additional patients to account for a 10% drop off rate, sample size for phase 2 study will be 35. Sample size analyses were conducted using the PASS software (NCSS, Kaysville, Utah, USA). With Phase 1b study component, the study will need to have 3 subjects from Dose Level 1 of Phase 1b + 6 subjects from Dose Level 2 of Phase 1b (and carried over to Phase 2 study).

TOTAL NUMBER OF SUBJECTS	Total number of subjects for the study is 38
ESTIMATED ENROLLMENT PERIOD	Estimated 18 months
ESTIMATED STUDY DURATION	Estimated 24 months

[figure not shown]
TABLE OF CONTENTS

ABBREVIATIONS	10
1. BACKGROUND AND RATIONALE.....	12
2 STUDY OBJECTIVES AND ENDPOINTS.....	13
3 ELIGIBILITY REQUIREMENTS	15
4 SUBJECT REGISTRATION	18
5 OVERALL DESIGN AND TREATMENT PLAN.....	18
6 DOSE DELAYS/DOSE MODIFICATIONS	24
7 STUDY CALENDAR & EVALUATIONS	28
8. CORRELATIVE STUDIES AND PROCEDURES.....	31
9. CRITERIA FOR DISEASE EVALUATION	33
11. ADVERSE EVENTS.....	39
12 STATISTICAL CONSIDERATIONS.....	45
13 TRIAL MANAGEMENT	49
14 DATA HANDLING AND RECORD KEEPING	51
15 ETHICS.....	52
16 REFERENCES	53
APPENDIX 1: ECOG PERFORMANCE STATUS	55
APPENDIX 2: DRUG INTERACTIONS WITH ENTRECTINIB.....	56

PHASE 1b SCHEMA

The primary objective of the Phase Ib study is to establish the maximum tolerated dose (MTD) of PAC-1 in combination with entrectinib for subjects with metastatic uveal melanoma, by evaluation of toxicity and tolerability.

Phase 1b

[figure not shown]
Dose Level*	PAC-1 Dose (mg, orally)	Entrectinib (mg, orally)	# of Subjects [#]
-1	625 daily	400 daily	3-6
1	625 daily	600 daily	3-6
2	750 daily	600 daily	3-6

*MTD cohort will be initially expanded to 6 patients, and if no DLT, to Phase 2 study.

PHASE 2 SCHEMA

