5.1.1 Dose Escalation Rules and MTD Definition

- Three subjects will initially be enrolled at dose level 1. If none of the 3 subjects experience a dose limiting toxicity (DLT) during the first cycle of therapy, three subjects will be enrolled at dose level 2. If all subjects in dose level 2 complete the first cycle of therapy without DLT, 3 more subjects will be enrolled into dose level 2 to ensure only 0-1 of 6 subjects have a DLT. There will be no further escalation beyond dose level 2.
- Alternatively, if 1 of the first 3 subjects within a dose level cohort experiences a DLT, the cohort will be expanded to 6 subjects. If this happens within dose level 1 and only 1 of the total 6 subjects in dose level 1 experience DLT, the study will proceed to dose level 2. If 2 or more of 6 subjects in a cohort experience DLTs, or 2 subjects within a cohort of 3 subjects experience DLT during the first cycle of therapy (>33% of subjects experiencing DLT), the MTD is exceeded. If this occurs at dose level 1, additional subjects will be accrued to dose level -1. If this occurs at dose level 2, 3 additional subjects will be

enrolled into dose level 1, unless there have been 6 subjects already enrolled into dose level 1.

- The MTD of PAC-1 in combination with entrectinib is the highest tested dose of PAC-1 combined with entrectinib with DLT rate of less than 33% in the first cycle of therapy (i.e., ≤ 1 out of 6 subjects with DLT). That dose will be recommended for the Phase 2 study.
- At the discretion of the sponsor-investigator, a lower Phase 2 dose may be recommended if other toxicity emerges during the Phase 1b study which does not meet DLT criteria but limits the dose that can be administered cumulatively.

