12.3.1 Number of subjects to be enrolled

Number to be enrolled:

Phase 1b: minimum of 9, maximum of 12

Phase 2: 6 subjects from MTD level in Phase 1b and an additional 29 subjects for a projected sample size of 35.

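### The single stated total of 38 subjects holds only if Phase 1b enrols 9; Section 12.3.1 allows 9 to 12, which makes the total 38 to 41

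*Combined protocol and SAP*

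**What the plan says.** Section 12.3 gives one study total: "The total number of subjects for the study is 38". The synopsis has the same figure: "Total number of subjects for the study is 38". Section 12.3 also shows the Phase 1b path behind it: "the study will need to have 3 subjects from Dose Level 1 of Phase 1b + 6 subjects from Dose Level 2 of Phase 1b", with the latter group carried into Phase 2.

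Section 12.3.1 gives the components separately. For the first part it has "Phase 1b: minimum of 9, maximum of 12". For Phase 2 it has "6 subjects from MTD level in Phase 1b and an additional 29 subjects for a projected sample size of 35". It gives no overall total.

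Section 5.1.1 explains how Phase 1b can exceed 9: "if 1 of the first 3 subjects within a dose level cohort experiences a DLT, the cohort will be expanded to 6 subjects". If Dose Level 1 expands in this way and only 1 of its 6 subjects has a DLT, the study goes on to Dose Level 2, which itself needs 6 subjects to be declared the MTD.

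**The concern.** Two adjacent subsections disagree. Section 12.3.1 holds the number of new Phase 2 subjects at 29 and lets Phase 1b vary, so the total must vary with it. Section 12.3 and the synopsis give one value with no range, and it matches only the smallest Phase 1b that Section 12.3.1 allows.

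The total is the number that anyone planning or overseeing enrolment would take from the synopsis. If Phase 1b uses 12 places, the trial must either go past its stated total or take fewer than 29 new subjects into Phase 2, which carries the primary efficacy endpoint. The plan does not say which.

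**Working it through.** **Inputs.** Phase 1b 9 to 12; 6 carried over; 29 additional; Phase 2 size 35 (Section 12.3.1). Powered size 32, 3 added for 10% drop-off, null rate 0.38, alternative 0.65, one-sided 0.05, power 90% (Section 12.3).

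**1. Reproduce the plan's figures.**
- Phase 2: 32 + 3 = 35, and 35 − 6 = 29 new subjects.
- Total: 3 + 6 + 29 = 38. This matches.
- Powered size: Section 12.3 names the software but not the test, so I assume an exact one-sample binomial test. At n = 32 it rejects at 18 or more, with type I error 0.027 and power 0.888. A normal approximation with continuity correction gives n = 31. The stated 32 for about 90% is acceptable.

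**2. Total as Phase 1b varies.** Total = Phase 1b size + 29.

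| Phase 1b | Total | Phase 2 size if 38 were a cap (38 − Phase 1b + 6) |
|---|---|---|
| 9 | 38 | 35 |
| 10 | 39 | 34 |
| 11 | 40 | 33 |
| 12 | 41 | 32 |

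Only 9 gives 38.

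**3. Effect on power if 38 were a cap and Phase 1b used 12.** New subjects: 38 − 12 = 26. Phase 2: 26 + 6 = 32, which is 3 fewer than 35. After 10% drop-off: 32 × 0.9 = 28.8 evaluable. Without the cap: 35 × 0.9 = 31.5.

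| Evaluable n | Reject at | Type I error | Power at 0.65 |
|---|---|---|---|
| 28 | ≥16 | 0.031 | 0.857 |
| 29 | ≥16 | 0.045 | 0.902 |
| 31 | ≥17 | 0.042 | 0.913 |
| 32 | ≥18 | 0.027 | 0.888 |

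Exact power moves up and down with n because the cut-off is a whole number. Against 0.888 at the planned 32, the change is 0.857 − 0.888 = −3.1 points at 28 and 0.902 − 0.888 = +1.4 points at 29.

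**4. How often Phase 1b ends at 12.** The documents give no DLT rates for the combination, so these are assumptions. Applying the Section 5.1.1 rules with DLT rates at Dose Levels 1/2 of:
- 5%/5%: about 16% of runs end at 12
- 5%/10%: about 21%
- 10%/15%: about 35%
- 20%/30%: about 50%

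Some of these runs end at Dose Level −1 or with no MTD: about 19% of the 12-subject runs at 10%/15% and 36% at 20%/30%, taking Dose Level −1 rates of 5% and 10%.

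**5. Is 12 the maximum under Section 5.1.1?** Take 3 at Dose Level 1 without a DLT, then 3 or 6 at Dose Level 2 with the MTD exceeded, then 3 more at Dose Level 1 with 2 or more of 6 now affected, then 3 or 6 at Dose Level −1. The largest case is 6 + 6 + 6 = 18. Two others give 15 (6 + 3 + 6 and 6 + 6 + 3). Under the assumed rates, about 3% of runs or fewer go past 12.

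**The case against.** The best defence is that 38 is the total for the path Section 12.3 spells out, with no expansion at Dose Level 1, and is correct for that path. Section 12.3.1 supplies the Phase 1b maximum and does not make the 29 depend on it, so a careful reader can work out 38 to 41 with Phase 2 still at 35. This largely stands. It shows that the intention can be recovered, but not that the stated total is right: Section 12.3 and the synopsis give 38 without calling it a minimum or an expected value.

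A reader might go further and infer that 38 is an enrolment ceiling, so that Phase 2 will lose 3 subjects and power will drop from 90% to 85.7%. The documents do not support that. Nowhere is 38 called a cap. The 85.7% applies only at 28 evaluable, while 28.8 is nearer 29, where power is 90.2%. And the like-for-like comparison is with 88.8%, the exact power at the planned 32, not the nominal 90%.

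A reader might also take the 35% to 50% frequencies as the chance that Phase 2 is short. They rest on assumed DLT rates and fall to about 16% to 21% at lower ones. They also include runs that end at Dose Level −1 or with no MTD. Sections 5.2 and 12.5.1 describe Phase 2 and the MTD with entrectinib at 600 mg, so those runs do not lead to the Phase 2 as written.

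**Conclusion.** The inconsistency is real and follows from the plan's own numbers: the total is 38 to 41, and the single figure understates it by up to 3 subjects. This part needs no assumption.

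The consequence for Phase 2 is conditional and small. It arises only if 38 is treated as a cap. In the worst case that Section 12.3.1 allows, Phase 2 enrols 32, which equals the powered number but leaves nothing for drop-off. Exact power after 10% drop-off is then about 86% to 90%, assuming an exact binomial test. If 38 is only a projection, Phase 2 keeps its 35 and only the headline figure is wrong.

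The range of 38 to 41 itself depends on the maximum of 12 in Section 12.3.1. The Section 5.1.1 rules can exceed that maximum, though rarely under the assumed DLT rates.

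**What to change.** In Section 12.3 and the synopsis, restate the total as 38 to 41 (9 to 12 in Phase 1b plus 29 additional in Phase 2), and state that the 29 additional Phase 2 places are kept whatever Phase 1b uses.

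Reconcile the Phase 1b maximum of 12 in Section 12.3.1 with the rules in Section 5.1.1, under which de-escalation from Dose Level 2 to 1 to −1 can reach 15 to 18. Which passage should change is for the sponsor to decide; the total should then follow from it.

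The cost is a wording change in two places plus that reconciliation. The restated total adds no subjects beyond those Section 12.3.1 already allows, and the analysis and error rates do not change. If an oversight body has approved 38 as a limit, which the documents do not show, that limit would need updating before enrolment reaches it.
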